#### **6.3.5 Removal of Individual Participants from Therapy or Assessments**

The following may result in a participant being removed prematurely from study participation:

- A participant withdraws consent to participate in the study.
- A participant was erroneously included in the study.
- The study is terminated by the Sponsor.
- A participant is unable to comply with study procedures (e.g., under the influence of drugs or alcohol or participant is combative)

#### **6.4 Objective**

To evaluate the ease of use and confidence with using the lebrikizumab pen to administer an injection using the Modified Subcutaneous Administration Assessment Questionnaire (mSQAAQ) following training on the pen.

## 7 TREATMENTS

No treatment will be administered; this will be a simulated test to evaluate the ease of use of the lebrikizumab pen.

### **Study Device Storage and Accountability**

The investigator or designee must confirm appropriate storage conditions have been maintained during transit for all study devices received and any discrepancies are reported and resolved before use of the study device.

Only participants enrolled in the study may receive study device. Only authorized study personnel may supply, prepare, or administer study device.

All study devices must be stored in a secure, environmentally controlled, and monitored (manual or automated) area in accordance with the labeled storage conditions with access limited to the investigator and authorized study personnel.

The investigator or authorized study personnel are responsible for study device accountability, reconciliation, and record maintenance, that is, receipt, reconciliation, and final disposition records.

Further guidance and information for the final disposition of unused study devices are provided in the Pharmacy Manual.

## 8 MATERIALS

The following materials will be used in the study:

### 8.1 Training Video

Participants will be provided with training in the use of the device prior to their simulated injection experience. This training will include an instructional video specific to describing parts of the lebrikizumab pen, pen operation instructions, and a demonstration of dose delivery into an injection pad.

### 8.2 Instructions for Use

Instructions for Use document will be provided together with the pen. The participant training will include a review of the IFU and the participant will be permitted to refer to these instructions during their simulated injection experience.

### 8.3 Lebrikizumab Pen and Injection Pad

Participants will be provided with a lebrikizumab pen that has been brought to room temperature for at least 45 minutes prior to the simulation. An injection pad will be provided for the simulated injection and participants will be instructed in the placement of the injection pads for the simulation.

### 8.4 mSQAAQ Questionnaire

After the simulated injection, the participant will be provided with a self-administered questionnaire, the mSQAAQ. This modified, short questionnaire, is an instrument that includes 10 questions about the ease of use and confidence in using the pen. The instructions for completion are embedded within the questionnaire. Participants will read the instructions before responding to the items in the mSQAAQ.

This tool is comprised of 10 questions. Responses are scored on a 7-point Likert scale ranging from ‘strongly disagree’ to ‘strongly agree:’

- (1) Strongly disagree; (2) Disagree; (3) Slightly Disagree; (4) Neither agree nor disagree;
- (5) Slightly agree; (6) Agree; (7) Strongly agree

## 9 INVESTIGATIONAL PLAN

### 9.1 Visit Schedule

This study will require one visit. Participants will be enrolled and completed at Visit 1. A Study Flowchart can be found in [Figure 2](#) and a Schedule of Events is located in [Table 2](#).

### 9.2 Details of Study Procedures

#### 9.2.1 Recruitment and Pre-Screening

Participants will be recruited by the research site who will access their site database comprised individuals who have participated in previous studies and/or expressed interest in participating in future studies. Potential participants will be pre-screened by phone with the inclusion and exclusion criteria including any previous pen experience. Participants who qualify (i.e. inclusion criteria apply, and exclusion criteria do not apply) will be referred to the research site.

#### 9.2.2 Visit 1

This is a single center, single visit simulated use study. All participants will be completed at the end of Visit 1. There is no treatment period; this study involves a simulated injection with a pen device into an injection pad followed by a self-administered questionnaire (mSQAAQ) about the participant's experience.

#### 9.2.3 Enrollment and Visit 1 Activities

Participants arriving at the research site will be given an informed consent document to read and sign. The participant will be given an opportunity to ask any questions and will be reminded that participation is voluntary and that the option exists to withdraw at any time. Inclusion and exclusion criteria will be re-confirmed as well as demographic information and previous pen experience; for this study, all participants are required to be pen and AI naïve (i.e., no prior experience with a pen or AI).

Participants who were assigned female at birth (AFAB) will be asked to take a urine pregnancy test to confirm they are not pregnant. Individuals not of childbearing potential (INOCBP) will be exempt from a urine pregnancy test. Individuals AFAB are considered INOCBP if they are not capable of producing ova or embryo, and/or are not capable of potentially gestating a fetus. Such individuals include those who have a congenital anomaly such as Müllerian agenesis resulting in confirmed infertility, are infertile due to surgical sterilization, or are menopausal. Acceptable surgical sterilization methods are hysterectomy, bilateral salpingo-oophorectomy, bilateral salpingectomy, or bilateral oophorectomy.

The Rapid Estimate of Adult Literacy in Medicine (REALM) test will be administered to assess health literacy. A brief medical history will be conducted to gather information about the approximate date of participants' AD diagnosis and any previous or current AD treatments. No laboratory assessments will be required, and no samples will be taken from study participants. Participants will then be given a brief study overview about the nature of the study in which they will simulate use of the pen into an injection pad.

#### **9.2.4 Device Training**

Training will be provided to participants in advance of the simulated injection. This training will be in the form of a clinical study training video describing parts of the lebrikizumab pen, pen operation instructions, and a demonstration of dose delivery into an injection pad. Study staff will also provide additional training and guidance such as introducing study materials to the participant, directing participant to review the IFU, assisting with attachment of the injection pad, and providing the mSQAAQ following injection simulation. Participants will be allowed to ask questions on training instructions to site staff during training.

#### **9.2.5 Simulated Injection**

[figure not shown]
Participants will be provided with IFU ([Appendix 14.1](#)), an injection pad and a pen device. The pen device will be taken out of the refrigerator at least 45 minutes prior to the simulation. The injection pad will be placed on the participant's thigh or abdomen, based on their preference. Participants will be directed to simulate an injection using the pen device by injecting directly into the injection pad.

The pen device contains active drug. Should a participant inadvertently stick themselves with the needle, follow-up care will be provided and an Adverse Event CRF and Product Complaint Form (if applicable) will be completed. Devices involved in product complaints or adverse events will need to be labeled and stored by site for future investigation by the Sponsor. Adverse events will be gathered from the point that the informed consent is signed until participant leaves site on date of visit. Participants with adverse events during the Visit will be followed for 7-days post visit (See [Section 12](#)).

#### **9.2.6 mSQAAQ**

After the simulated injection, participants will be provided with a self-administered questionnaire, the mSQAAQ to complete. After the mSQAAQ is completed, the visit will be completed.

**Figure 2: Study Flowchart**

**Table 2 Schedule of Events**

Activity	Prescreening	Visit 1	Post-Visit 1( If needed)
Prescreening (inclusion/exclusion, demographics, confirm date of diagnosis)	X		
Check ID		X	
Assign a participant ID number		X	
Administer Informed Consent		X	
Reconfirm Inclusion/Exclusion Criteria and demographics		X	
Confirm AI and pen naïve (PFS permitted)		X	
Pregnancy test for participants AFAB unless considered INOCBP		X	
Medical history including approximate date of the participant's AD diagnosis, any previous or current AD treatments		X	
Administer the REALM Test		X	
Provide a study overview		X	
Provide training on the device, including training video		X	
Participant performs simulated injection (into injection pad)		X	
Self-administered mSQAAQ		X	
Product complaints and adverse events management		X	X
End-of-Visit		X	

## 10 DATA COLLECTION, MANAGEMENT, AND ANALYSIS

### 10.1 Data Collection

Case Report Form (CRF) data will be collected using a 21 CFR Part 11 compliant electronic data capture system (EDC), the IQVIA Research Management Platform (RMP) v2.6. Data from recruitment and pre-screening will be captured separately and not entered into the RMP EDC system. Since the study is being conducted in person, a paper informed consent and a paper 24-hour SAE report form will be used.

CRF data will include:

- Confirmation of inclusion and exclusion criteria
- Participant demographics
- REALM score
- Confirmation of pen/AI experience (i.e., pen/AI naïve, any other experience with injectables)
- Pregnancy test results for participants AFAB unless considered INOCBP
- Brief medical history (approximate date of AD diagnosis and previous or current treatments)
- Responses to the 10 questions in the mSQAAQ
- Adverse events (AE)
- Serious adverse events (SAE)

### 10.2 Sample Size

The planned final sample size of 51 is sufficient to provide descriptive insights about the study population. Given the nature of the study it is expected that CCI%+ of participants enrolled will complete the study and provide full analyzable data.

Under the assumption that CCI% of the participants will respond “agreed” or “strongly agreed” to the device being “easy to use” and “they are confident they can use the device” we will have 95% confidence that the response rate is located in this range of proportions: [CCI% - CCI%]. Table 3 shows a variety of possible sample sizes. For the purpose of the intended claims the 95% CI lower bound should remain above CCI%, preferably above CCI%, and the parameters for the calculation of sample size have been selected for that.

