## 2 STUDY SYNOPSIS

Name of Company: Eli Lilly & Company (Lilly)
Protocol Number: #23037 (J2T-MC-KGBY)
Name of Investigational Product/Active Ingredients: Lebrikizumab Pen
Title of Study: Study to Assess Lebrikizumab Pen Ease of Use in Patients with Atopic Dermatitis
Name of Contract Research Organization (CRO): Concentrics Research, an IQVIA Business
Participant Environment: The participant environment will be non-clinical and emulate the noise, lighting, and surroundings of a home environment. Study rooms are equipped with 1-way mirrors, cameras, and remote monitoring equipment for participant observation. There will be 1 research site used in this study.
Study Type: Ease of use with a simulated injection
Objective: To evaluate the ease of use and confidence of lebrikizumab administrations via a prefilled pen using the modified Subcutaneous Administration Assessment Questionnaire (mSQAAQ)  following training on the pen.
Design This study is an open-label, single site ease of use study of the lebrikizumab pen and consists of a single study visit for approximately 51 adult participants. All participants will receive training and perform simulated injections on an injection pad using the pen. Participants will be under the supervision of study site staff when handling the pen and will complete the mSQAAQ  following the simulated injection. No treatment will be administered to the participants.
Study Population The study population will be comprised of adults, ages 18 and older, who have been diagnosed with Atopic Dermatitis (AD). These participants will be pen and autoinjector (AI) naïve (i.e., not previously used a pen or AI); however, they will be permitted to participate if they have other injection experience (e.g., pre-filled syringe [PFS]).
Recruitment One research site will be used for this study, the Concentrics Center for Research in Indianapolis, IN. Participants will be recruited from the site's database. Approximately 56 participants will be enrolled with 51 participants planned to complete the study. Recruitment will include telephone prescreening based on the inclusion and exclusion criteria and collection of demographics. A broad range of participants will be recruited to assure racial and ethnic diversity that approximates the U.S. Census. 

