### **Sample Size**

The planned analysis population for this descriptive study is 51 participants. Sample size was calculated based on the following assumptions: CC1 95% of the participants will respond “agreed” or “strongly agreed” to each individual mSQAAQ  question, with associated 95% confidence intervals. No comparative analyses are planned for this study.

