**Table 3      Sample Size Calculation**

Proportion	Margin	Lower CI	Upper CI	Sample Size
95.0%				
95.0%				
90.0%				
85.0%				
80.0%				

Table 4 shows the possible 95% confidence intervals (CI) if the response rate does not reach the assumed 95%. All sample sizes have been calculated with the shown assumptions for proportion of response, margin of error, and a 95% confidence interval.

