6. GENERAL CONSIDERATIONS

6.1 Sample Size

The planned final sample size of 51 participants with full data is sufficient to provide descriptive insights about the study population. Given the nature of the study it is expected that **cci**%+ of participants enrolled will complete the study and provide full analyzable data.

As defined in the protocol, under the assumption that **cci**% of the participants will respond “agreed” or “strongly agreed” to the device being “easy to use” and “they are confident they can use the device” we will have 95% confidence that the response rate is located in this range of proportions: **cci**% - **cci**%. [Table 1](#) shows a variety of possible sample sizes. For the purpose of the intended claims the 95% CI lower bound should remain above **cci**%, preferably above **cci**%, and the parameters for the calculation of sample size have been selected for that.

Table 1 Sample Size Calculation

Proportion	Margin	Lower CI	Upper CI	Sample Size
95.0%				
95.0%	CCI			
90.0%				
85.0%				
80.0%				

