7. STATISTICAL CONSIDERATIONS

7.1 Statistical Tests and Confidence Intervals

Continuous variables will be summarized using descriptive statistics, i.e., by the number of non-missing and missing observations, mean, standard deviation (SD), first quartile (Q1), median, third quartile (Q3), minimum, and maximum.

Categorical variables will be summarized by frequency counts (n) and percentages (%). Percentages will not include the missing category and are calculated over the number of patients with available (non-missing) data. Counts of missing data will be provided in the tables for information only.

For reporting conventions, percentages will be reported to 1 decimal place unless greater precision is deemed appropriate, except for cases when 100% is presented. In cases of a count of 0, the percentage will not be presented. The 95% confidence interval (CI) for the response rates will be calculated using Clopper-Pearson method.

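### Was the sample of 51 sized with a different confidence interval from the Clopper-Pearson interval that the SAP will report?

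*Protocol*

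**What the plan says.** Protocol 10.2 states: "The planned final sample size of 51 is sufficient to provide descriptive insights about the study population". It then assumes a proportion of participants who agree or strongly agree, gives a 95% range for it (redacted), and adds: "For the purpose of the intended claims the 95% CI lower bound should remain above CCI%, preferably above CCI". The words CCI stand where the sponsor has blacked out numbers.

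The text under Protocol Table 3 describes the method only in general terms: "All sample sizes have been calculated with the shown assumptions for proportion of response, margin of error, and a 95% confidence interval". It also identifies the planning rate: "Table 4 shows the possible 95% confidence intervals (CI) if the response rate does not reach the assumed 95" (per cent). In Tables 3 and 4 only the Proportion column can be read; the margin, both limits and the sample size are redacted.

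SAP 6.1 repeats the argument and the first of these tables, and says of the lower-bound aim: "and the parameters for the calculation of sample size have been selected for that". It names no formula either. SAP 7.1 does name one for the analysis: "The 95% confidence interval (CI) for the response rates will be calculated using Clopper-Pearson method".

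Two further statements set the context. The synopsis says under Recruitment: "Approximately 56 participants will be enrolled with 51 participants planned to complete the study". Under Sample Size it says: "No comparative analyses are planned for this study".

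**The concern.** Near 95%, the choice of interval matters. The normal approximation is symmetric and runs past 100%. The exact interval is asymmetric and reaches further down. A study sized with the first and reported with the second would show a lower bound several points below its planning figure.

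Two features of the text point that way. The tables carry a single margin column, which suits a symmetric interval. And 51 is exactly what the textbook formula gives for 95% with a 6-point margin. Since the lower bound is tied to intended claims, a sponsor expecting about 89% could be surprised by 84% to 87% from a result close to 95%.

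**Working it through.** **Inputs.** n = 51 (Protocol 10.2); assumed response p = 0.95 (text under Protocol Table 3); 95% confidence, taken as two-sided, z = 1.96; Clopper-Pearson at analysis (SAP 7.1). The margin is redacted, so whole-point margins are assumptions.

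**Step 1: can 51 be reproduced?** Plain normal approximation, n = z²p(1−p)/m², with z²p(1−p) = 3.8415 × 0.0475 = 0.18247:

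| Assumed margin m | n | Rounded up |
|---|---|---|
| 5 points | 72.99 | 73 |
| 6 points | 50.69 | 51 |
| 7 points | 37.24 | 38 |
| 8 points | 28.51 | 29 |

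A 6-point margin reproduces 51. At n = 51 the margin is 1.96 × √(0.0475/51) = 5.98 points, so the interval is 89.0% to 101.0%.

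**Step 2: do other formulas fit?**

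- Continuity-corrected normal approximation: the half-width at n = 51 is 5.98 + 100/(2 × 51) = 5.98 + 0.98 = 6.96 points, and at n = 50 it is 7.04. A 7-point margin therefore also gives 51, with a lower bound of 88.0%.
- Clopper-Pearson at exactly 95% (x = 0.95 × 51 = 48.45, treated as continuous): the lower limit is the 2.5% quantile of Beta(48.45, 3.55) = 84.99%, and the upper limit is the 97.5% quantile of Beta(49.45, 2.55) = 99.14%. To one decimal, the precision of the readable Proportion column, this is 85.0% to 99.1%. The half-width is (99.14 − 84.99)/2 = 7.07 points. Strict targets of 85% for the bound or 7 points for the half-width need n = 52, so 51 misses the 85% target by 0.01 point.
- Wilson: a half-width of 6 or 7 points needs 60 or 46, and a lower bound of 85% needs 49.

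Three constructions therefore fit 51, and the readable text does not separate them.

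**Step 3: how large would a mismatch be?** Lower bounds at n = 51:

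| Responders | Plain normal | Clopper-Pearson | Gap (points) |
|---|---|---|---|
| 95% exactly (48.45) | 89.0% | 85.0% | 4.0 |
| 48/51 (94.1%) | 87.7% | 83.8% | 3.9 |
| 49/51 (96.1%) | 90.8% | 86.5% | 4.2 |
| 46/51 (90.2%) | 82.0% | 78.6% | 3.4 |
| 43/51 (84.3%) | 74.3% | 71.4% | 2.9 |

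Against the continuity-corrected version, the gap at 95% is 88.0 − 85.0 = 3.0 points. If the sizing used Clopper-Pearson, the gap is zero.

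**Step 4: would a claim threshold be missed?** This needs the redacted thresholds. For illustration only, at a true rate of 95% and n = 51, the chance that one item's lower bound exceeds an assumed 80% is 0.89 by Clopper-Pearson (47 or more responders) and 0.96 by the plain normal approximation (46 or more). For an assumed 85% it is 0.53 (49 or more) and 0.75 (48 or more). The result turns on the assumed threshold, so nothing can be concluded about the real one.

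**The case for a change.** The case for acting is that redaction removed numbers, not sentences: the sentences describing the calculation are readable and name no method. The single margin column does suit a symmetric interval, since Clopper-Pearson at n = 51 lies about 10 points below 95% and 4 above. Enrolling 56 would not close the gap if all completed: 53/56 and 54/56 give Clopper-Pearson lower bounds of 85.1% and 87.7%, still under 89%. And the sponsor could name the formula in one sentence.

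The omission is real, and so is the arithmetic. The inference is weaker. It fits one hidden margin to one sample size, after several formulas and targets have been tried. The plain normal reading needs an upper limit of 101.0%, which would have to be printed as impossible or cut at 100%. A margin column can equally hold a half-width or the distance to the lower bound; for Clopper-Pearson that distance is 95 − 84.99 = 10.01 points. Anyone holding the unredacted tables sees margin and both limits side by side: 89.0% with 101.0% (or 100%) points to one formula, 85.0% with 99.1% to the other. Much of the doubt belongs to the public copy rather than to the plan.

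One could also ask for the minimum number of responders per claim threshold and the chance of reaching it. That may be useful to a sponsor, but a descriptive precision study need not state it, and the request does not follow from an unnamed formula.

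**Conclusion.** No change is needed. The sizing text leaves its interval formula unnamed, and that is a gap in detail rather than a demonstrated error. If a normal approximation was used, the planned lower bound at 95% is about 3 to 4 points above what Clopper-Pearson will give. If Clopper-Pearson was used, there is no difference. The documents support either reading.

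The outcome of the trial is the same in both cases. The SAP fixes the reported interval before analysis, that interval is valid, and an analyst following SAP 7.1 has nothing to decide. There is no hypothesis test, so no error rate or power is affected, and the concern itself gives no reason to alter n = 51. Naming the formula would tidy the record without changing any result.

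This rests on the study being descriptive, as both documents state, and on the redacted figures being present and legible in the sponsor's copy. It does not establish that the claim thresholds will be met; the public text cannot settle that in either direction.

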**Table 3      Sample Size Calculation**

Proportion	Margin	Lower CI	Upper CI	Sample Size
95.0%				
95.0%				
90.0%				
85.0%				
80.0%				

Table 4 shows the possible 95% confidence intervals (CI) if the response rate does not reach the assumed 95%. All sample sizes have been calculated with the shown assumptions for proportion of response, margin of error, and a 95% confidence interval.

